## 9. LISTINGS

- List of patients
- List of patients with adverse drug reactions
- List of patients with serious adverse drug reactions
- List of patients with serious adverse events
- List of patients with adverse events
- List of time to malignant tumor, serious infection and death, and censoring period
- List of patients with adverse drug reactions among patients excluded from the safety analysis
- List of patients with adverse drug reactions among patients with hepatic dysfunction
- List of patients with adverse drug reactions among patients with renal dysfunction
- List of patients with adverse drug reactions among the elderly
- List of patients with adverse drug reactions among pregnant and parturient women
- List of efficacy endpoints
- List of surgical therapies for rheumatoid arthritis
- List of patients excluded from analysis (patients aged 16 years or younger, patients receiving Xeljanz for conditions other than rheumatoid arthritis)
- List of patients with serious infection

- List of patients with neutrophil count decreased and neutropenia
- List of patients with lymphocyte count decreased and lymphopenia
- List of patients with lipid increased and hyperlipidemia
- List of patients with malignant tumors (including lymphoma)
- List of patients with gastrointestinal perforation
- List of patients with cardiovascular adverse events
- List of patients with hepatic dysfunction
- List of patients with interstitial pneumon
- List of patients with opportunistic infection
- List of patients with herpes zoster
- List of patients with tuberculosis
- List of patients with pneumocystis pneumonia
- List of concomitant medications used in patients with herpes zoster
- List of deaths (Patients in which death was selected as the reason for discontinuation of treatment or investigation, patients in which death was selected in the seriousness of adverse events, and patients in which adverse events leading to death occurred.)
- List of contraindicated patients with adverse drug reactions

In addition, the following tables corresponding to Appendix Forms of periodic safety update reports will be prepared:

- Appendix Form 3 (list of the summary of included patients)
- Appendix Form 2 (list of the development of adverse drug reactions and infections)
- Appendix Form 10 (Appendix Form 2-2) (list of the development of serious adverse events)

## 11. APPENDICES

### 11.1. Appendix 1: Details of Data Extraction

#### 11.1.1. Definition of Visit Timing

Day 1: In the Xeljanz group, the oldest initiation date in the status of administration of Xeljanz.

In the control group, the oldest initiation date in the status of drug administration.

Visit timing	Evaluation item	Definition [acceptance range]
Before the initiation of administration	Laboratory test Blood pressure Efficacy observation items	= 'Date of assessment' - 'Date Day 1' + 1 = [-30 - 1] Target date = 1
1 month after the initiation of administration	Laboratory test Blood pressure Efficacy observation items	= 'Date of assessment' - 'Date Day 1' + 1 = [2 - 62] Target date = 31
3 month after the initiation of administration	Laboratory test Blood pressure Efficacy observation items	= 'Date of assessment' – 'Date Day 1' + 1 = [63- 138] Target date=92
6 month after the initiation of administration	Laboratory test Blood pressure Efficacy observation items	= 'Date of assessment' – 'Date Day 1' + 1 = [139- 230] Target date=184
9 month after the initiation of administration	Laboratory test Blood pressure Efficacy observation items	= 'Date of assessment' – 'Date Day 1' + 1 = [231- 321] Target date=275
12 month after the initiation of administration	Laboratory test Blood pressure Efficacy observation items	= 'Date of assessment' – 'Date Day 1' + 1 = [322- 412] Target date=366
15 month after the initiation of administration	Laboratory test Blood pressure Efficacy observation items	= 'Date of assessment' – 'Date Day 1' + 1 = [413- 503] Target date=457
18 month after the initiation of administration	Laboratory test Blood pressure Efficacy observation items	= 'Date of assessment' – 'Date Day 1' + 1 = [504-595] Target date=549

Visit timing	Evaluation item	Definition [acceptance range]
21 month after the initiation of administration	Laboratory test Blood pressure Efficacy observation items	= 'Date of assessment' – 'Date Day 1' + 1 = [596- 686] Target date=640
24 month after the initiation of administration	Laboratory test Blood pressure Efficacy observation items	= 'Date of assessment' – 'Date Day 1' + 1 = [687- 777] Target date=731
27 month after the initiation of administration	Laboratory test Blood pressure Efficacy observation items	= 'Date of assessment' – 'Date Day 1' + 1 = [778- 868] Target date=822
30 month after the initiation of administration	Laboratory test Blood pressure Efficacy observation items	= 'Date of assessment' – 'Date Day 1' + 1 = [869- 960] Target date=914
33 month after the initiation of administration	Laboratory test Blood pressure Efficacy observation items	= 'Date of assessment' – 'Date Day 1' + 1 = [961- 1051] Target date=1005
36 month after the initiation of administration	Laboratory test Blood pressure Efficacy observation items	= 'Date of assessment' – 'Date Day 1' + 1 = [1052-1142] Target date=1096

If there are multiple data corresponding to 1 visit label, priority will be given to the date closest to the target date. If there are multiple closest dates, priority will be given to the date before the target date.

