## 2 Subjects

Among rheumatoid arthritis patients with poorly controlled disease in spite of continuous use of a methotrexate preparation (hereinafter, MTX) in a dosage exceeding 8 mg/week for 3 months or more, those meeting the following criteria:

- 1) All patients who receive Xeljanz (Xeljanz group)
- 2) Patients who have begun pharmacotherapy with another drug\* (control group)

\*Patients with no experience of treatment with Xeljanz (Patients participating in clinical trial cannot be registered in the control group)

When using Xeljanz, refer to “Guidelines for the use of tofacitinib in all-cases post-marketing surveillance” (revised version on June 29, 2014) (Japan College of Rheumatology) (hereinafter, “tofacitinib use guidelines”). Please consider using a pharmacotherapy other than Xeljanz for patients who do not meet the criteria shown below.

[Target patients]

1. Rheumatoid arthritis patients with poorly controlled disease in spite of continuous use of a methotrexate preparation (MTX) in a dosage exceeding 8 mg/week for 3 months or more. Patients with the above treatment history after February 23, 2011 when the approved dosage for MTX was increased to 16 mg/week are targeted. However, it is desirable not to target patients to whom MTX cannot be administered from the safety perspectives at this point, in principle.
  - Painful joint count of 6 or more
  - Swollen joint count of 6 or more
  - CRP of 2.0 mg/dL or more or ESR of 28 mm/hr or more
 Even if patient does not meet the 3 criteria above, consider use if there is moderate or higher activity for any of
  - DAS28-ESR, SDAI, and CDAI.
2. Moreover, out of consideration for safety with respect to opportunistic infections, it is strongly recommended that the following 3 criteria be met.
  - Peripheral blood count of 4000/mm^3 or more
  - Peripheral lymphocyte count of 1000/mm^3 or more
  - Negative for blood β-D-glucan

Excerpted from “tofacitinib use guidelines”

The indication and dose regimen for this Surveillance are as follows: (This surveillance targets rheumatoid arthritis patients with poorly controlled disease in spite of continuous use of a methotrexate preparation (MTX) in a dosage exceeding 8 mg/week for 3 months or more.)

- Indication: Patients with rheumatoid arthritis who showed inadequate response to conventional treatments
- Dosage and Administration: As a standard therapy, a patient should receive a daily oral administration of tofacitinib 5 mg BID.

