### 6.4 Patient registration

[1] After the date on which the contract for this Surveillance is concluded, the investigator conducting surveillance will complete the registration form provided by Sponsor, and submit the form to Patient Registration Center via FAX.

[Patient Registration Center]

[contact]

Business hours: 9:00 to 17:15 (except for Saturdays, Sundays, National Holidays, and New Year Holidays)

\*FAX transmission after 16:00 will be responded during the following business day.

[2] Definition of start date

(1) Xeljanz group

The date on which administration of Xeljanz begins will be considered the “start date of treatment.” However, for patients participating in the clinical trial, the start date will be considered the date on which administration of the commercially available Xeljanz product begins, and in the case of subjects administered Xeljanz at other medical facilities, it will be the date on which treatment at the physician’s own hospital begins.

(2) Control group

For rheumatoid arthritis patients with poorly controlled disease in spite of continuous use of a methotrexate preparation (MTX) in a dosage exceeding 8 mg/week for 3 months or more, the date on which the change in pharmacotherapy began is regarded as the “start date of surveillance.”

[3] Enrollment method

(1) Xeljanz group

The registration form should be submitted to the Patient Registration Center via FAX in principle no later than 1 week prior to the start of Xeljanz therapy.

If the sponsor has made the judgment that there has been a deviation from the scope of proper use of Xeljanz on the basis of the registration information, this will be checked with the physician in charge of surveillance, and the proper use information will be explained. If any of the patients registered in the control group has been administered Xeljanz during the registration period, the patient will also need to be registered in the Xeljanz group.

(2) Control group

The registration form should be faxed to the Case Registration Center within 2 weeks after surveillance start in the control group.

In principle, case selection in the control group should be performed according to the prescribing conditions for routine medical care under actual use conditions.

Patients to whom any of the following apply will be excluded from candidates for registration in the control group.

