##### [11] Laboratory tests (peripheral leukocyte count, peripheral lymphocyte count, $\beta$ -D-glucan)

2) Survey form

(1) Patient characteristics prior to and at the start of treatment

The following will be recorded for both treatment groups.

[1] Height/weight

[2] Inpatient/outpatient status

Indication (Patients with rheumatoid arthritis), stage and grade (Steinbrocker stage), and functional class (Steinbrocker functional class)

[3] Duration of disease

[4] Clinical history (past history and concurrent illness)

[5] History of smoking (history of smoking at treatment start)

[6] Family history of malignant tumor

(2) Previous treatment drugs for rheumatoid arthritis (3 months before treatment start)

The following will be recorded for both treatment groups.

[1] MTX

- Past use (presence/absence)
- Weekly dosage
- Duration of treatment

[2] Oral steroid use for rheumatoid arthritis

- Past use (presence/absence), period or treatment

[3] Tacrolimus

- Past use (presence/absence)
- Duration of treatment

(3) Dose record

[1] Xeljanz group

Number of doses per day, treatment period, reason for change (if there has been a change in administration)

[2] Control group

If there has been a switch to another type of pharmacotherapy, excluding Xeljanz, during the observation period, the case will be handled as a continued surveillance case, and the treatment record should be continuously entered.

In cases where Xeljanz has been administered, surveillance as a member of the control group will be handled as discontinued, and registration in the Xeljanz group will be necessary.

● MTX

Name of drug (name of product), weekly dosage, and duration of treatment

● Pharmacotherapy with drugs other than MTX (biological preparation, DMARDs, immunosuppressants, oral steroid preparations)

Name of drug (name of product), daily dosage (oral steroids), and duration of treatment

(4) Concomitant therapy (Xeljanz group)

For drug therapy, covering the period starting 3 months prior to the start of treatment in this Surveillance

and ending at the completion or discontinuation of the observation period will be completed. Medications used for the treatment of adverse events should also be recorded.

[Concomitant therapies coadministered with Xeljanz]

- [1] MTX
- [2] Biological preparations\*
- [3] DMARDs other than MTX and immunosuppressants\*
- [4] Oral steroid
- [5] Other drugs

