### **5.1.2. Comparison of the Xeljanz group and the control group**

- Comparative analysis set

Of the enrolled patients with a scheduled observation period of 3 years, those who were confirmed to treat Xeljanz in the Xeljanz group and a control drug (control drug is MTX, biological agents, DMARDs or immunosuppressive drug) at least once were included in the control group. The patients who apply to a to f in Section 5.1.1 are excluded.

The control group also excludes patients who do not meet the MTX criteria and patients who have been treated with Xeljanz.

- MTX adherent comparative analysis set

The MTX adherent comparative analysis set of the Xeljanz group is the patients who meets the MTX criteria among the new patients of the comparative analysis set.

As for the control group, since the comparative analysis set of the control group is limited to the patients who meet the MTX criteria, the same set is also used as the control group of MTX adherent comparative analysis set.

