**Table 4. Categories of Tabulation Items for Administration Status**

Item	Category	Note
Total dose [mg]	No category	Continuous data Xeljanz group only
Average daily number of administrations [time/day]	$\leq$ once, $>$ once to $\leq$ twice, $>$ twice to $\leq$ 3 times, $>$ 3 times	Xeljanz group only
Average daily dose [mg]	$\leq$ 5mg, $>$ 5 mg to $\leq$ 10 mg, $>$ 10 mg	Xeljanz group only
	$<$ 7.5mg, $\geq$ 7.5mg	
Average daily number of actual administrations [time/day]	$\leq$ once, $>$ once to $\leq$ twice, $>$ twice to $\leq$ 3 times, $>$ 3 times	Xeljanz group only
Average actual daily dose [mg]	$\leq$ 5mg, $>$ 5 mg to $\leq$ 10 mg, $>$ 10 mg	Xeljanz group only
	$<$ 7.5mg, $\geq$ 7.5mg	
Drugs initially administered	MTX, biological products, DMARDs or immunosuppressants, MTX + biological products, MTX + DMARDs or immunosuppressants, biological products + DMARDs or immunosuppressants, MTX + biological products + DMARDs or immunosuppressants	Control group only  Drugs which are written in “Status of drug administration” within 7 days from the oldest date of commencement

- Tabulation and analysis of each subset

Patient characteristics will be tabulated for each subgroup sorted by the initial daily dose in Xeljanz group (5 or 10 mg). Also, for each subgroup sorted by the initial daily dose, patient characteristics will be further tabulated for new patients started in this surveillance, patients who took part in clinical study, patients transferring from other hospital, subpopulation that meets the MTX criteria, and subpopulation that does not meet the MTX criteria.

Items for which the calculation will be made are shown in “[Appendix 11.1.2 Patient Background](#)”.

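### SAP 11.1.1 starts control follow-up at the oldest date in the drug record, not at the protocol's change of therapy, so pre-switch time could enter control person-time

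*SAP*

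**What the plan says.** The two documents give controls different time zeros.

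- Protocol 6.4 [2](2): for controls, "the date on which the change in pharmacotherapy began is regarded as the" start date of surveillance. Item [7] of the registration form (Protocol 7.1) collects that date for every control.
- SAP 11.1.1, Day 1: "In the control group, the oldest initiation date in the status of drug administration". For the Xeljanz group the same appendix uses the oldest start date of Xeljanz itself. The control rule is tied neither to a particular drug nor to the switch.
- SAP Tables 5, 6 and 7 count time to malignant tumor, serious infection and death from the treatment-initiation date. They do not define that date for controls and do not cite 11.1.1.
- Protocol 7.1, survey form item (3), puts MTX in the control dose record: "Name of drug (name of product), weekly dosage, and duration of treatment". Oral steroids, biologics, DMARDs and immunosuppressants are recorded there too, also with duration.
- SAP 5.1.2 counts MTX among the control drugs: "control drug is MTX, biological agents, DMARDs or immunosuppressive drug".
- SAP Table 4 takes a control's initial drugs as those recorded "within 7 days from the oldest date of commencement".
- Footnote *5 to the schedule in Protocol section 7 makes control events reportable only from the start of surveillance: 12 months for serious infection, 36 months for malignant tumor and death.

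**The concern.** Entry requires disease that is poorly controlled despite MTX "in a dosage exceeding 8 mg/week for 3 months or more". Some controls will therefore have taken MTX, and perhaps oral steroids, before the switch and will continue them afterwards. Neither document says that an entry in the control drug record must begin at the switch. If a continuing drug is entered with its true start date, SAP 11.1.1 read literally puts Day 1 before the change of therapy.

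That earlier time cannot contain a reportable event. It would enlarge the control denominator and lower the control rate. New Xeljanz patients, the only Xeljanz patients in the main comparison set, have no matching lead. The Xeljanz/control ratio would then rise with no true difference, and propensity weighting on baseline covariates cannot repair a wrong time zero.

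Serious infection has a second problem. Its time is limited to one year from treatment initiation (366 days in four rows of Table 6). A Day 1 set too early would push real control infections late in the first year after the switch outside the window. The initial-drug tabulation in Table 4 would be affected in the same way: a long-term MTX user who adds a biologic could be tabulated as MTX alone.

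**Working it through.** **The plan's own figure.** Inputs from the sample-size rationale (Protocol section 3): 1.16 malignant tumors per 100 person-years, about 50% drop-out at 3 years, 4000 Xeljanz patients, 104 expected events. With drop-out linear over time, mean follow-up is 3 × (1 − 0.5/2) = 2.25 years. Then 4000 × 2.25 = 9000 person-years, and 9000 × 0.0116 = 104.4 events, which reproduces 104.

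**Controls with Day 1 at the switch.** 2000 × 2.25 = 4500 person-years and 4500 × 0.0116 = 52.2 events. The rate is 1.16 per 100 person-years and the ratio 1.00. By the SAP 8.1.6 formula, the standard error of the log ratio is √(1/104.4 + 1/52.2) = 0.170, giving a 95% CI of 0.72 to 1.39.

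**Malignancy with a lead.** Let L be the event-free lead in years. It is an assumption, given to all controls, with a true ratio of 1. Follow-up is taken to end relative to the switch, as in the protocol; the overall-observation rows of Table 5 set no numeric limit. Control rate = 52.2 / (4500 + 2000 L), and ratio = (2.25 + L) / 2.25. The last column is the chance that a two-sided 5% test of a true ratio of 1 rejects, by normal approximation: Φ(ln ratio / 0.170 − 1.96) + Φ(−ln ratio / 0.170 − 1.96).

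| L (years) | Control person-years | Rate per 100 | Ratio (95% CI) | Chance of rejection |
|---|---|---|---|---|
| 0 | 4500 | 1.16 | 1.00 (0.72–1.39) | 5% |
| 0.25 | 5000 | 1.04 | 1.11 (0.80–1.55) | about 10% |
| 0.5 | 5500 | 0.95 | 1.22 (0.88–1.70) | 22% |
| 1 | 6500 | 0.80 | 1.44 (1.04–2.01) | 58% |

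The pairing of 2400 controls with 3000 Xeljanz patients gives the same ratios.

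**Serious infection, one-year limit.** Assume constant hazard and no drop-out. Events can occur only in the last 1 − L of the window, while person-time stays close to one year, so the ratio is about 1/(1 − L): 1/0.75 = 1.33 at L = 0.25 and 1/0.5 = 2.0 at L = 0.5. The documents give no infection rate. With assumed rates of 2 to 10 per 100 person-years and exact person-time, a 92-day lead gives 1.34 to 1.35 and a half-year lead 2.0. At a lead of one year or more, no infection after the switch falls inside the window.

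**Only some controls affected.** For a share f, replace L by f × L in both approximate formulas (L up to one year for infection). Half the controls with a half-year lead gives 2.5/2.25 = 1.11 and 1/0.75 = 1.33. With f = 0 both ratios are 1.

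**The case against.** The strongest reply is that the control drug record was meant to open at the switch, so the two anchors coincide in practice. There is real support for this.

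- Earlier MTX, steroid and tacrolimus use has its own survey block, "Previous treatment drugs for rheumatoid arthritis (3 months before treatment start"), separate from the dose record.
- The schedule in Protocol section 7 appears to run the dose record from the start of surveillance.
- For concomitant therapy in the Xeljanz group the protocol says expressly that the record reaches back 3 months. It says nothing of the kind for the control dose record.
- Table 4 has combination categories such as MTX with a biologic. A 7-day window from the oldest date makes sense for these only if the record opens at the switch.
- Day 1 sits in a visit-timing appendix whose rows cover laboratory tests, blood pressure and efficacy items, and Tables 5 to 7 do not cite it.

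These points stand as evidence of intent, and they make the bias conditional. They do not remove the conflict. No sentence truncates entries at the switch, SAP 11.1.1 is the SAP's only explicit start date for controls, and SAP 8.2.2 applies that appendix's target dates to the control drug tabulation.

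A reader might infer more than the documents support:

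- That Day 1 is the oldest drug date anywhere on file. SAP 11.1.1 names one section of the record.
- That time before registration is at fault. Controls register "within 2 weeks after surveillance start in the control group", and the stretch from switch to registration is valid follow-up. The time at issue lies before the switch.
- That the lead is at least 3 months. Protocol section 2 accepts a qualifying MTX history from any time after February 23, 2011, so MTX need not be current, and SAP 11.1.2 allows for no MTX use in the prior 3 months. An entry may also begin at a recent dose change.
- That the comparison is in fact biased. The case report form is not in the documents, so neither the share affected nor the lead is known.

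**Conclusion.** The conflict between the protocol and SAP anchors is established from the text. The bias is possible, not shown. If it occurs, it is likely to raise the Xeljanz/control ratio, because pre-switch control time is free of reportable events and new Xeljanz patients have no such time. Its size runs from nil, if every control record opens at the switch, upward with the share of controls affected and the length of the lead. The ratios of 1.11 and 1.22 for malignancy, and of about 1.33 and 2.0 for one-year serious infection, rest on a constant hazard, a true ratio of 1 and an assumed lead of 0.25 or 0.5 year for all controls. They are illustrations, not estimates. SAP section 4 calls all tests exploratory, so the practical harm would be a shifted estimate more than a failed decision rule. Because time zero underlies both comparisons named in the objective, and the right date is already collected, this should be fixed.

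**What to change.** In SAP 11.1.1 and 8.2.3.1, define both control Day 1 and the control treatment-initiation date used in Tables 5 to 7 as the protocol's start date of surveillance (registration item [7]). State that drug entries starting earlier do not set it. Use the same date as the anchor for the 7-day window in Table 4.

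Then count the controls whose oldest record date precedes item [7], and report the count with the distribution of the gap. If there are none, the change is wording only. If there are any, re-run the malignancy, serious-infection and death comparisons from the corrected date.

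The cost is a few sentences of SAP text, one derivation and one check. No new data are needed.
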